9.13 Overdose

An overdose is defined as a subject receiving a dose of avelumab in excess of that specified in the protocol.

Any overdose of a study subject with avelumab, with or without associated AEs/SAEs, is required to be reported within 24 hours of knowledge of the event to Pfizer using the contact for SAE reporting. If the overdose results in an AE, the AE must be recorded as an AE. Overdose does not automatically make an AE serious, but if the consequences of the overdose are serious, for example death or hospitalization, the event is serious and must be recorded and reported as a SAE. There is currently no specific treatment in the event of an overdose of avelumab. The investigator will use clinical judgment to treat any overdose of avelumab.

9.14 Pregnancy

Pregnancy itself, or pregnancy of a subject's partner, is not regarded as an AE unless there is a suspicion that the investigational product under study may have interfered with the effectiveness of contraception. Elective abortions without complications should not be handled as AEs. The outcome of any conception occurring from the date of the first dose until 90 days after the last dose (spontaneous miscarriage, elective termination, ectopic pregnancy, normal birth or congenital abnormality) should be followed up/document even if the subject was withdrawn from study.

Pregnancy in a female subject who has received investigational product is required to be reported ***within 24 hours of knowledge of the event*** to the sponsor and Pfizer Patient Safety or designee using the designated safety contact provided under the SAE reporting section.

Subjects who become pregnant during the study period must not receive additional doses of investigational product but will not be withdrawn from the study. The pregnancy will be followed for outcome of the mother and child (including any premature terminations) and should be reported to Pfizer Patient Safety or designee after outcome.

Males should refrain from fathering a child or donating sperm during study and for 90 days following the last dose of avelumab.

Should the investigator become aware of a pregnancy in the partner of a male study subject who has received investigational product this should be reported ***within 24 hours of knowledge of the event*** to Pfizer Patient Safety or designee using the safety contact provided under the SAE reporting section. The sponsor will endeavor to collect follow-up information on such pregnancies provided the partner of the study subject provides consent.

The full details of reporting for any pregnancy that occurs while exposed to avelumab is described in the Pfizer *Safety Reporting Reference Manual*.

10. STATISTICAL METHODS

10.1 Study design and sample size

This is a single arm, non-randomized window of opportunity study to see the change in T cell subpopulations (CD8, CD4 and/or CD3) in tumor samples collected pre- and post-treatment with avelumab. Assuming that pre- and post-treatment values within patients are moderately correlated ($r \geq 0.5$), then 10 patients with paired pre- and post-treatment samples will provide ~80% power to detect a 1 standard deviation change in T cell populations (alpha=5% two-tailed).

10.2 Statistical analysis

To see the change in T cells pre- and post-treatment, paired t-test or nonparametric Wilcoxon signed rank test will be used after checking its normality.

Pathological response rate will be estimated along with 95% confidence interval. Two year disease free survival will be calculated using Kaplan-Meier survival curves with estimates of median and 95% confidence interval. Patients who are decided not to be evaluable for the primary outcome will be considered evaluable for the safety analysis and secondary outcomes, such patients will be summarized descriptively. The correlation of translational studies with response parameters will be summarized descriptively. Changes from pre- and post- treatment will be assessed using paired tests. SAS software will be used for all statistical analyses.

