2. STUDY OBJECTIVES

2.1 Primary objective(s)

- To evaluate change in T cell subpopulations (CD8, CD4 and/or CD3) in tumor samples collected pre- and post-treatment with avelumab.

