2.3 Translational endpoints

- To evaluate PD-L1 by IHC and COX-1/COX-2 expression by mRNA in pre- treatment cancer tissues (focusing on epithelial cell expression and immune cell expression).
- To evaluate infiltrating CD3+, CD4+ and CD3+, CD8+ T cells in pre- and post- PD-L1 antibody treated patient cancer tissues by IHC.
- To evaluate change in regulatory B-cell populations with treatment as identified by IHC for CD1d, CD5, CD19 and CD24.
- To evaluate mRNA levels of the following chemokines/cytokines and immune checkpoints on formalin fixed paraffin embedded (FFPE) tissue from pre- and post- treatment specimens: IFN- γ , TNF- α , TNF- β , T-box protein in B-cells (T-bet), IL-2, IL-10, IL-35, FOXP-3, CTLA-4, LAG-3, PD-L1, Granzyme-A and Perforin-1.

[figure not shown]

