7.3.1 Biomarker evaluation methods

Immunohistochemistry:

Concentrations of PD-L1 protein expression on tumor cells or other cell types (e.g. immune cells) will be measured by IHC analysis of FFPE tissues from the TURBT and RC specimens. PD-L1 expression will be assessed using one of the following anti-human-PD-L1 antibodies, depending on initial studies of the relative staining patterns on serial sections: SP142 (Spring Bioscience) (64), SP263 (Ventana Medical Systems), or E1L3N (Cell Signaling Technologies). (65) PD-L1 levels will be evaluated according to the percentage of positively stained cells based on a score ranging from 0 to 3: 0 = <1%; 1 = 1 to <5%; 2 = 5 to <10%; 3 = >10% of cells positive. (66)

FFPE tissue from TURBT and RC specimens will also be stained with primary antibodies for lymphocytic markers CD1d, CD3, CD4, CD5, CD8, CD19 and CD24. This will be

followed by staining with a secondary antibody for horseradish peroxidase and then DAB or blue chromogranin. The results of these lymphocyte IHC stains will be appraised using a semiquantitative scale scored according to the percentage of positively stained cells in tumor or stroma as follows: 0=none, 1 = up to 33% cells in tumor were positive, 2 = 33-66% positive cells and 3=more than 66% cells positive. (67) Tissue sections will be scored by at least two independent staff pathologists.

RNA Extraction from FFPE Tissue:

We have compared three different methodologies head-to-head for extraction of high quality RNA from FFPE tissues, namely ThermoFisher (PureLink™ FFPE RNA Isolation Kit), Clontech (NucleoSpin® totalRNA FFPE) and Covaris (truXTRAC FFPE RNA Kit). Covaris FFPE RNA extraction resulted in the highest quality RNA, sufficient for downstream qPCR and even RNA seq analysis. The main advantages of the Covaris protocol includes its efficiency to completely deparaffinize without using high-temperature enzymatic degradation (which also degrades RNA) and the overall shorter time required to complete the overall protocol. Thus we will extract RNA from FFPE tissue using the protocol for the Covaris truXTRAC FFPE RNA Kit.

qRT-PCR:

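### The primary test is chosen by a normality check on 10 differences of a 0-3 score; this costs power, and with integer scores and an exact signed-rank test the choice can change the verdict

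*Protocol*

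**What the plan says.** - **Objective.** Section 2.1 sets the primary objective: "To evaluate change in T cell subpopulations (CD8, CD4 and/or CD3) in tumor samples collected pre- and post-treatment with avelumab". Section 2.3 gives the assay: "To evaluate infiltrating CD3+, CD4+ and CD3+, CD8+ T cells in pre- and post- PD-L1 antibody treated patient cancer tissues by IHC".
- **Scale.** Section 7.3.1 grades the lymphocyte stains, CD3, CD4 and CD8 among them, as "0=none, 1 = up to 33% cells in tumor were positive, 2 = 33-66% positive cells and 3=more than 66% cells positive". At least two pathologists score each section. No rule for combining their scores is given, and no continuous T-cell measure is described.
- **Sample size.** Section 10.1 assumes that "pre- and post-treatment values within patients are moderately correlated" (r of at least 0.5) and says "10 patients with paired pre- and post-treatment samples will provide ~80% power" "to detect a 1 standard deviation change in T cell populations", with "alpha=5% two-tailed".
- **Test.** Section 10.2 says "paired t-test or nonparametric Wilcoxon signed rank test will be used after checking its normality".

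**The concern.** A data-driven choice between the paired t-test and the signed-rank test matters little for a continuous, roughly normal variable, because the two usually agree. Here the difference between two scores can take only the values -3 to +3. Such differences cannot be normal. In 10 patients, whether a check rejects normality depends largely on how the ties and zeros happen to fall.

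On this scale the two tests also behave differently. An exact signed-rank test that drops zeros has a floor on its p-value set by the number of patients whose score changes. The t-test has no such floor. The preliminary check can therefore settle the primary verdict, and the power of the whole procedure need not be that of the t-test behind section 10.1.

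**Working it through.** **1. The plan's own figure.** Inputs from section 10.1: n = 10 pairs, r = 0.5, change of 1 SD, two-sided 5%.

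- SD of the difference = SD × √(2(1 − 0.5)) = 1 SD.
- Noncentrality = √10 × 1/1 = 3.16, with 9 degrees of freedom.
- Paired t-test power from the noncentral t = 80.3%. The stated ~80% is reproduced, for a paired t-test on a continuous normal variable.

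**2. The floor of the exact signed-rank test.** With k non-zero differences the smallest two-sided p is 2/2^k.

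- k = 5: 2/32 = 0.0625.
- k = 6: 2/64 = 0.031.

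So p < 0.05 is out of reach when five or fewer patients change score.

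**3. Two worked samples.**

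- Five patients at +1 and five at 0. Mean 0.5, SD = √(2.5/9) = 0.527, t = 0.5/(0.527/√10) = 3.0, p = 0.015. Exact signed-rank p = 0.0625.
- Seven at +1, two at 0, one at −1. Mean 0.6, SD = √(4.4/9) = 0.699, t = 2.71, p = 0.024. Exact signed-rank: 2 × (1 + 8)/256 = 0.070.

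**4. How often this happens.** Ten differences can fall on seven values in C(16,6) = 8,008 ways. Each was tested with the paired t-test, the exact signed-rank test (zeros dropped, mid-ranks for ties) and a Shapiro-Wilk check at 5%. The Shapiro-Wilk check is an assumption, since the protocol names none. The two-step rule uses the signed-rank test if the check rejects and the t-test otherwise. The 8,008 outcomes were weighted by probabilities from a bivariate normal (r = 0.5) cut into four levels. The baseline shares of scores 0/1/2/3 are assumptions, as the protocol gives none.

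Shift set so that mean/SD of the score differences = 1:

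| Baseline shares, % | t-test power | Exact signed-rank power | Two-step rule power | Tests disagree |
|---|---|---|---|---|
| 25/25/25/25 | 81.2% | 66.2% | 72.0% | 15.0% |
| 30/50/15/5 | 79.1% | 63.9% | 71.2% | 15.2% |
| 20/65/12/3 | 79.5% | 61.3% | 66.8% | 18.3% |
| 15/35/35/15 | 79.4% | 63.9% | 71.0% | 15.5% |

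- Power lost by the rule against the t-test: 81.2 − 72.0 = 9.2 points, 79.1 − 71.2 = 7.9, 79.5 − 66.8 = 12.7 and 79.4 − 71.0 = 8.4.
- The check rejects normality in 45%, 61%, 76% and 62% of trials respectively, so the branch varies from sample to sample.
- In essentially every conflict the t-test is significant and the signed-rank test is not.
- With a shift of 1 SD on the underlying normal scale instead, the tests disagree in 17-22% of trials.
- For comparison, a continuous normal variable with the same n and mean/SD = 1 gives conflict in 4.7% of trials and two-step power of 80.1%.

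**5. Type I error (no shift).** Two-step rule 0.6-2.8%; exact signed-rank test 0.5-1.7%. For the t-test it is 4.1-4.5% across these four shapes and two more (20/50/20/10 and 10/60/20/10).

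**6. Sensitivity to what the protocol leaves open.**

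- Two readers' scores averaged to half steps (assumed reader noise 0.3 SD, shift of 1 underlying SD): conflict in 9-12% of trials.
- Normal approximation for the signed-rank test: conflict in 2-3%.

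**The case against.** Several objections have force.

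- **The ~80% in section 10.1 is not wrong for this scale.** A reader might infer that it fits neither test once the data are 0-3 scores, because a 1 SD shift on the underlying normal scale gives the t-test only 60-68% power. That comparison uses a smaller effect than section 10.1 states. For shares of 15/35/35/15, for example, the score differences then have mean 0.806 and SD 0.928, a ratio of 0.87 and not 1. With the ratio set to 1 the t-test recovers 79-81%. Only the signed-rank test and the two-step rule fall short.
- **No excess of false positives.** A reader might expect a data-driven choice of test to inflate type I error. Here it does not; the rule is conservative.
- **The conflict rate is conditional.** It needs integer scores and an exact signed-rank test. Section 7.3.1 does not say how readers are combined, and section 10.2 does not say exact or approximate. It would go too far to say without these conditions that the choice often decides the trial.
- **The five-and-five example shows that the tests differ, not that the choice is arbitrary there.** Shapiro-Wilk gives p = 0.0003, so under that check the rule clearly selects the signed-rank test.
- **Detail may sit in an analysis plan that is not shown.** Which normality check is used, and its cut-off, can be left to that plan and is no finding. The data-driven choice itself is written in the protocol.
- **This is a 10-patient pilot** with no stated go/no-go criterion, which limits the consequences. It still states a formal two-sided 5% test with a power figure for its primary objective.

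**Conclusion.** The point holds in a limited form. Section 10.2 lets a preliminary check that carries little information on 10 small-integer differences select the primary test. With integer scores and an exact signed-rank test, the two candidates give opposite verdicts in about 15-20% of trials near the design effect.

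The cost is a verdict that hangs on that check, and about 8 to 13 points of power: 67-72% for the rule as written against 79-81% for the paired t-test. The exact signed-rank test alone has about 61-66%. These figures are for one marker and rest on assumed score distributions, r = 0.5 and a Shapiro-Wilk check at 5%; the shapes tried agree closely. Under reader averaging or a normal approximation the conflict is smaller. The change is worth making because it is cheap and gains power without exceeding the 5% level in any setting tried.

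**What to change.** In section 10.2, delete the normality step and name one primary test before any data are read. One candidate is the paired t-test on the change in score. Report the exact signed-rank test as a stated sensitivity analysis. In section 10.1, say that the power refers to the named test on the 0-3 scale, and that the 1 SD change is expressed on the score differences.

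The cost is a sentence in each section, with no extra patients, samples or procedures. The downside is that the t-test treats an ordinal score as numeric. If the signed-rank test is preferred for that reason, it can be named instead, but the stated power should then fall to about 61-66%.

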11. ETHICAL AND REGULATORY REQUIREMENTS

11.1 Ethical conduct of the study

The study will be performed in accordance with ethical principles that have their origin in the Declaration of Helsinki and are consistent with the International Conference on Harmonization (ICH) /Good Clinical Practice, and applicable regulatory requirements for subject data protection.

11.2 Ethics and regulatory review

Avelumab is an investigational drug not approved for clinical use in patients with bladder cancer. Our study will undergo review by the BCM Institutional Review Board (IRB). Investigational New Drug applications will also be filed with the FDA.

11.3 Informed consent

Informed consent shall be documented by the use of a written consent form approved by the IRB and the sponsor. This consent form shall be signed and dated by the subject or the subject's legally authorized representative at the time of consent. A copy shall be given to the person signing the form.

11.4 Changes to the protocol and informed consent form

Any changes to the protocol or informed consent form will be reviewed by the sponsor and the local IRB prior to implementation. Any changes to the informed consent form that impact currently enrolled subjects (e.g., changes in procedures, changes in the benefit/risk profile) will require that subjects are re-consented with the new consent form.

11.5 Audits and inspections

All records and documents pertaining to the study will be maintained in appropriate permanent files as per the ICH guidelines for Essential Documents for the Conduct of a Clinical Trial and 21

CFR 11, and will be available for inspection by the Sponsor, Sponsor designee, the FDA, or any other designated review body at any time.

12. STUDY MANAGEMENT

The principal investigator assumes all oversight and reporting of the study, including the training of study site personnel and monitoring of the study.

12.1 Training of study site personnel

The PI of this study will train the study coordinator in the procedures necessary to identify and accrue appropriate individuals to the study. The PI of the study will also train the staff scientist in the lab on appropriate tissue collection and storage procedures. The PI will train infusion center staff on appropriate administration of study drugs.

12.2 Monitoring of the study

Subjects will be monitored closely throughout the course of the study via regular visits with the study PI and direct access to the PI throughout the duration of the study. The PI is directly responsible for the study subjects, and the study staff will be instructed to contact the PI immediately with any concerns regarding patient safety or other matters.

12.3 Study timetable and end of study

The end of the study will be defined as the time point 90 days after RC. The recruitment period is estimated to take place over a period of approximately 12 months.

13. DATA MANAGEMENT

The database that will be utilized for data collection and storage will be OnCore. The PI and study staff will adhere to the reporting requirements of the data to the institutional IRB.

14. DATA AND SAFETY MONITORING AND QUALITY ASSURANCE

This study will be monitored regularly by the Data Review Committee (DRC) of the Dan L. Duncan Comprehensive Cancer Center, at a frequency of at least once per year, in accordance with the DLDCCC Data and Safety Monitoring Plan. The DRC will monitor the study for progress and enrollment, toxicities, adverse events, and soundness of data.

This study will be monitored by the DLDCCC Quality Assurance program for study conduct and quality of data.

